## **9.5 Analysis of the Secondary Endpoints**

The effect of knowledge of a positive *APOL1* status on secondary endpoints [i.e., change in urine microalbuminuria/proteinuria orders from baseline to 6 months (Y/N), documented order of microalbuminuria/proteinuria tests by 6 months (Y/N), change in documented diagnosis for stage 3 CKD and above (Y/N) from baseline to 6 months, documented diagnosis of CKD stage 3 and above by 6 months (Y/N), change in documented diagnosis for any stage CKD from baseline to 6 months (Y/N), and documented diagnosis of all stages of CKD by 6 months (Y/N) ] will be compared between Intervention - *APOL1* positives and Control - *APOL1* positives with the proportion difference test.

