## **9.9 Multiplicity**

With the primary and various secondary endpoints that have been outlined, there is a multiplicity of analyses to be performed, which leads to an increased probability that at least one of the comparisons could be "significant" by chance. Adjusting for the effects of the repeated significance testing for the multiplicity of secondary endpoints would require that very small significance levels be used for every comparison. Therefore, rather than adjusting for multiple comparisons, statistical results (e.g., p values) will only be presented for the primary endpoint analysis. We will be conservative in the interpretation of secondary analyses and report only point estimates and 95% confidence intervals. We have also pre-specified the primary and secondary outcome variables to avoid over-interpretation of strictly exploratory comparisons.

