### 10.2 Data Element Definitions

Baseline SBP will be defined as the mean of the 2nd and 3rd measurements taken according to the GUARDD-US Blood Pressure Protocol provided in the MOP. Similarly, follow-up SBP will be the average of the 2nd and 3rd SBP measures at the follow-up visit, or alternatively the SBP from the EHR entered into the study database by the site in accordance with the study manual of procedures (MOP).

Secondary Endpoints will be defined as follows:

1. Change in urine microalbuminuria/proteinuria orders from baseline to 6 months (Y/N)
  - a. Order of urine microalbuminuria/proteinuria test at baseline is a binary variable (Y/N) where 'Y' is defined as the presence of urine proteinuria or urine microalbuminuria diagnostic code (i.e. 82043/84156 (Current Procedural Terminology (CPT) codes) OR the presence of urine microalbuminuria/proteinuria lab test order and/or result in the participant's EHR record at any point in the 12 months prior to baseline.
  - b. Order of urine microalbuminuria/proteinuria test at 6 months is a binary variable (Y/N) where 'Y' is defined as the presence of urine proteinuria or urine microalbuminuria diagnostic code 82043/84156 (CPT codes) OR the presence of urine microalbuminuria/proteinuria lab test order and/or result in the participant's EHR record at any point from baseline to 6 months.

- c. Change in urine microalbuminuria/proteinuria orders is a binary variable (Y/N) where 'Y' is defined as no order of urine microalbuminuria/proteinuria test at baseline and having an order of urine microalbuminuria/proteinuria test at 6 months [No for 1a, Yes for 1b = NY].

2. Documented order of microalbuminuria/proteinuria tests by 6 months is a binary variable (Y/N) where 'Y' is defined as the change in urine microalbuminuria/proteinuria orders (as described in 1c) OR (order of urine microalbuminuria/proteinuria test at baseline) [NY, YN or YY]

3. Change in documented diagnosis for stage 3 CKD and above from baseline to 6 months (Y/N)

- a. Documented diagnosis at baseline is a binary variable (Y/N) where 'Y' is defined as [the presence of a CKD ICD10 diagnosis codes of N18.3 – N18.5 in the 24 months prior to baseline].
- b. Documented diagnosis at 6 months is a binary variable (Y/N) where 'Y' is defined as [the presence of a CKD ICD10 diagnosis codes of N18.3 – N18.6 in the 6 months after baseline].

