- c. Change in documented diagnosis for stage 3 CKD and above is a binary variable (Y/N) where 'Y' is defined as no documented diagnosis at baseline and documented diagnosis at 6 months [No for 3a, Yes for 3b = NY].

4. Documented diagnosis of stage 3 and above CKD by 6 months is a binary variable (Y/N) where 'Y' is defined as (change in documented diagnosis for stage 3 CKD (as described in 3c)) OR (documented diagnosis at baseline (as described in 3a)) [NY, YN or YY].

5. Change in documented diagnosis for any stage CKD from baseline to 6 months (Y/N)

- a. Documented diagnosis at baseline is a binary variable (Y/N) where 'Y' is defined as [the presence of a CKD ICD10 diagnosis code (i.e., N18.x; E08.22; E09.22; E10.22; E11.22; E13.22) in the 24 months prior to baseline].
- b. Documented diagnosis at 6 months is a binary variable (Y/N) where 'Y' is defined as [the presence of a CKD ICD10 diagnosis code (i.e., E18.x; E08.22; E09.22; E10.22; E11.22; E13.22) in the 6 months after baseline].
- c. Change in documented diagnosis for any stage CKD is a binary variable defined as no documented diagnosis at baseline and documented diagnosis at 6 months [No for 5a, Yes for 5b = NY].

6. Documented diagnosis of any stage CKD by 6 months is a binary variable (Y/N) where 'Y' is defined as (the change in documented diagnosis of any stage CKD (as described in 5c)) OR (documented diagnosis at baseline (as described in 5a)) [NY, YN or YY].

For CEA analyses, the following definitions for variables obtained from the EHR will be used:

1. 6-month CKD stage will be defined with the follow categories using the most recent GFR measurement obtained between baseline and 6 months:
  - a. Stage 1 with normal or high GFR (GFR > 90 mL/min)
  - b. Stage 2 Mild CKD (GFR = 60-89 mL/min)
  - c. Stage 3A Moderate CKD (GFR = 45-59 mL/min)
  - d. Stage 3B Moderate CKD (GFR = 30-44 mL/min)
  - e. Stage 4 Severe CKD (GFR = 15-29 mL/min)
  - f. Stage 5 End Stage CKD (GFR <15 mL/min)
2. 6-month blood cholesterol: The last observed blood cholesterol level observed prior to baseline. Missing values will be imputed.

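### Secondary endpoints 2, 4 and 6 score pre-baseline events as successes and are compared without adjustment for baseline status, which makes their 95% confidence intervals needlessly wide

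*Combined protocol and SAP*

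**What the plan says.** Section 10.2 builds the six secondary endpoints in three pairs: 1/2 for urine orders, 3/4 for stage 3 or higher CKD diagnosis, and 5/6 for any-stage CKD diagnosis.

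- The change endpoint of each pair (1, 3, 5) is Yes only for a participant who was No at baseline and Yes afterwards, for example "No for 1a, Yes for 1b = NY".
- The by-6-months endpoint (2, 4, 6) is Yes for that participant and also for everyone who was Yes at baseline. For endpoint 2 the added clause is "OR (order of urine microalbuminuria/proteinuria test at baseline) [NY, YN or YY", for endpoint 4 "OR (documented diagnosis at baseline (as described in 3a)) [NY, YN or YY", and for endpoint 6 "OR (documented diagnosis at baseline (as described in 5a)) [NY, YN or YY". The YN pattern, with an event before baseline and none after it, is a success.
- Baseline status for urine orders is any order or result "in the participant's EHR record at any point in the 12 months prior to baseline". For diagnosis it is a qualifying code "in the 24 months prior to baseline".

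Section 9.5 compares all six endpoints between the APOL1-positive groups "with the proportion difference test" and mentions no adjustment. Section 4.2 stratifies randomisation by clinical site only. Under Section 9.9, p-values are presented for the primary endpoint alone; for secondary analyses the trial will "report only point estimates and 95% confidence intervals".

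**The concern.** A participant who is Yes at baseline is a success on endpoint 2, 4 or 6 whatever happens after randomisation, so the intervention cannot move that outcome. The only randomised information in these endpoints comes from baseline-negative participants, and the paired change endpoint already carries it. What endpoints 2, 4 and 6 add to the arm comparison is the difference in pre-randomisation status, which is zero in expectation but not in any one trial.

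The baseline-positive share may be large. The codes in item 5a also establish CKD for eligibility in Section 5.1, and one pilot study cited in Section 9.1 estimated a CKD prevalence of 50%. Section 9.6 itself warns that baseline characteristics may differ between the APOL1-positive groups, yet it plans adjustment only for the SBP mixed models. At stake is how precisely secondary aims 1 and 2 are answered, and whether readers take each pair as two findings when it holds one comparison.

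**Working it through.** **Inputs from the documents.** Section 9.1 plans 469 APOL1-positive participants per arm (6700 × 0.14 = 938; 938/2 = 469). The plan states no power, effect or event rate for secondary endpoints, so its only checkable figure is the primary sample size. A 3.5 mm Hg difference, SD 18.1, two-sided alpha 0.0492 and 80% power give 422 per arm, or 844; 844/0.9 = 938. That reproduces.

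**Assumed inputs.** Let b be the share Yes at baseline and q the 6-month event rate among baseline-negatives. Neither is given.

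- Urine orders: q = 20% v 29%. These are the pilot's renal-testing rates from Section 2.1, which are 12-month figures and not restricted to baseline-negatives, so they are illustrative only.
- Diagnosis: q = 5% v 10%, purely assumed.

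**Step 1, the identity (no assumption needed).** New event and baseline Yes are disjoint, so the rate on endpoint 1 is (1−b)q and on endpoint 2 is b + (1−b)q. The observed arm difference on endpoint 2 is that on endpoint 1 plus the observed arm difference in baseline status. The same holds for 4 v 3 and 6 v 5. The expected differences within a pair are equal.

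**Step 2, size of the added term.** The 95% range of chance imbalance is ±1.96·√(2b(1−b)/469).

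| b | 95% range (points) |
|---|---|
| 20% | ±5.1 |
| 30% | ±5.9 |
| 40% | ±6.3 |
| 50% | ±6.4 |
| 60% | ±6.3 |

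**Step 3, variance per participant in one arm.**

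- Stratified by baseline status: (1−b)q(1−q). Baseline-positives are constant within both endpoints and contribute nothing.
- Endpoint 1 unadjusted: (1−b)q(1−q) + b(1−b)q².
- Endpoint 2 unadjusted: (1−b)q(1−q) + b(1−b)(1−q)².

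The extra terms are never negative, so in large samples the stratified estimate is at least as precise as either unadjusted one. Endpoint 2 minus endpoint 1 is b(1−b)(1−2q). Summed over arms, endpoint 2 is the less precise of the two only when the average q is below 50%.

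**Step 4, 95% CI half-widths in points, 469 per arm.** Stratified half-width = 1.96·√((1−b)[q_C(1−q_C) + q_I(1−q_I)]/469). For the first row: 1.96·√(0.7 × (0.1600 + 0.2059)/469) = 4.6.

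| Scenario | Expected difference | Change endpoint | By-6-months endpoint | Stratified |
|---|---|---|---|---|
| Urine, b = 30%, 20% v 29% | 6.3 | 4.8 | 6.4 | 4.6 |
| Diagnosis, b = 50%, 5% v 10% | 2.5 | 2.4 | 6.4 | 2.4 |
| High conversion, b = 30%, 60% v 69% | 6.3 | 6.4 | 5.5 | 5.1 |

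Estimating b for the weights adds δ²b(1−b)/(2 × 469) to the variance, where δ is the arm difference in q. That is under 1% of the variance in the first two rows.

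**Step 5, simulation (40,000 trials per scenario).** With no effect, rejection at 5% stays near 5% for both members of a pair (4.9% and 5.2% at b = 30%, q = 20%). In the first row, the correlation of the estimated effect with baseline imbalance is 0.69 for endpoint 2 and −0.30 for endpoint 1. In the diagnosis row it is 0.93 for the by-6-months endpoint.

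**The case against.** The definitions are explicit and deliberate: Amendment 5 added the YN pattern. Cumulative status is a coherent quantity for a chronic diagnosis, since a code entered before baseline remains documented even if not re-entered. Each by-6-months endpoint is paired with one that isolates new events, so the incident effect is already reported. All of that stands, and it is a reason to leave the definitions alone.

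A reader might infer that endpoints 2, 4 and 6 are biased or produce false positives. They do not: baseline status is balanced in expectation, type I error holds, and a valid interval already covers the imbalance. A reader might also infer that the trial loses power on them. Section 9.9 reports no p-values for secondary endpoints, so the practical consequence is interval width. A loss relative to endpoints 1, 3 and 5 also needs average conversion below 50%; the third row of the table reverses it.

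Nor are endpoints 1, 3 and 5 clean comparators, because baseline-positives stay in their denominator as failures.

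It is also tempting to replace endpoint 2 with item 1b (any order after baseline) for a gain in power. The 89% power that 1b would have with 20% v 29% in everyone assumes an effect in participants already tested. With the effect confined to baseline-negatives and an assumed 50% retest rate in both arms, 1b has 41% against 38% for endpoint 2 at b = 40%, and 20% against 22% at b = 60%. Redefining an endpoint in an unblinded trial after interim looks would also have a cost.

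Finally, Section 9.2 defers detail to a separate SAP, so the absence of adjustment is established only for this document.

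**Conclusion.** The point holds as one of avoidable imprecision. The identity and the precision advantage of stratification follow from the Section 10.2 definitions alone. The sizes rest on assumed rates: in the two main illustrations the half-width falls from 6.4 to 4.6 points (urine) and from 6.4 to 2.4 points (diagnosis) for the same expected difference. The gain over endpoints 2, 4 and 6 is largest where new events are rare, which is the likelier situation for CKD diagnosis. Once baseline status is accounted for, the two members of a pair give the same risk difference, so the six endpoints contain three randomised comparisons.

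**What to change.** Keep the Section 10.2 definitions. In Section 9.5, estimate one risk difference with its 95% CI for each pair (1/2, 3/4, 5/6), stratified by or standardised to baseline status (items 1a, 3a, 5a). Specify a stratified or standardised risk difference and not a logistic model: every baseline-positive is Yes by definition on 2, 4 and 6, so a logistic model would meet perfect prediction in that stratum. State that the adjusted result is the same for both members of a pair, and that endpoints 2, 4 and 6 add descriptive cumulative proportions by arm.

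Item 1b may be added as a supplementary analysis, because only it can show repeat testing of participants already tested. No power gain should be claimed for it.

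Before finalising the stratifier, reconcile the urine look-back, which is 24 months in Section 7.7 and 12 in item 1a.

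Cost: wording in Section 9.5 and the SAP. The components are already defined and collected. The small downside is that each pair is openly shown to carry one comparison, not two.

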Description of implementation of intervention (e.g., dose, schedule, etc.)	
The primary intervention for GUARDD-US is the immediate return of APOL1 genetic testing results to participants and participant providers. Return of APOL1 genetic testing results to participants and providers will occur as described in Section 7.6. In addition to verbal ROR, participants will also receive lay explanations in writing and an educational booklet explaining their results and genetic risks. Providers will be notified of participant results via standard site-specific laboratory return of results methods and, where possible, a clinical decision support system (CDS) within the electronic health system as described in Section 7.8. Providers may also receive links for accessing provider and participant educational materials through the CDS or other means. Finally, all participants are given the option to discuss their results with a genetic counselor.
 
The intervention for the PGx substudy is the immediate return of PGx testing results to participants via phone and/or in-person, return of results and alerts via standard site-specific laboratory return of results methods and a CDS within the electronic health system for providers, and educational materials for both patients and providers regarding the genes tested and phenotypes associated with the efficacy of hypertension medications.

Inclusion/Exclusion Criteria	
Inclusion Criteria:
 
 
● Self-reported African ancestry
 
● English Speaking
 

- Age 18-70 years
- Have diagnosis of hypertension
  - Diagnosis of hypertension is defined by either:
    - ICD10 diagnosis codes (i.e., I10; I11.x; I12.x; I13.x; I16.x) OR
    - On active antihypertensive therapy for indication of hypertension OR
    - Having systolic blood pressure of 140 mm Hg or greater in at least 2 of the last 3 consecutive recorded values in the EHR OR
    - Having hypertension in the patient's medical record problem list
- Have been seen at  $\geq 1$  time in past year at a participating primary care site
- Either: 1) do not have diabetes and do not have CKD, or 2) have CKD; Participants with diabetes may be included as long as they also have CKD.
  - CKD is defined by:
    - ICD10 codes (i.e., N18.x; E08.22; E09.22; E10.22; E11.22; E13.22 (exclude Z94.0; N18.6; Z99.2)) OR

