#### **3.2 Secondary Endpoints**

Secondary endpoints include:

1. Change in urine microalbuminuria/proteinuria orders from baseline to 6 months (Y/N)
2. Documented order of microalbuminuria/proteinuria tests by 6 months (Y/N)
3. Change in documented diagnosis for stage 3 CKD and above from baseline to 6 months (Y/N)
4. Documented diagnosis of CKD stage 3 and above by 6 months (Y/N)
5. Change in documented diagnosis for any stage CKD from baseline to 6 months (Y/N)
6. Documented diagnosis of all stages of CKD by 6 months (Y/N)

Please see Section 10.2 for the derivations of these endpoints.

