## 5. STUDY POPULATION

### 5.1 Inclusion Criteria

- Self-reported African ancestry
- English Speaking
- Age 18-70 years
- Have diagnosis of hypertension
  - Diagnosis of hypertension is defined by either:
    - ICD10 diagnosis codes (i.e., I10; I11.x; I12.x; I13.x; I16.x) OR
    - On active antihypertensive therapy for indication of hypertension OR
    - Having systolic blood pressure of 140 mm Hg or greater in at least 2 of the last 3 consecutive recorded values in the EHR OR
    - Having hypertension in the patient's medical record problem list
  - Have been seen at ≥1 time in past year at a participating primary care site
  - Either: 1) do not have diabetes and do not have CKD, or 2) have CKD; Participants with diabetes may be included as long as they also have CKD.
    - CKD is defined by:
      - A) ICD10 codes (i.e., N18.x; E08.22; E09.22; E10.22; E11.22; E13.22 (exclude Z94.0; N18.6; Z99.2)) OR
      - B) Microalbumin/proteinuria level >30 mg/g for 2 time periods ≥ 3 months. Values taken within 12 months of enrollment, unless 2 values are unavailable, then review within 24 months of enrollment.
        - 1) If there is only 1 proteinuria in E.H.R. (or if there are multiple and they are all within 3 months), any single proteinuria/microalbuminuria >30 mg/g would qualify
        - 2) If there are two or more proteinuria measures in E.H.R. that are at least 3 months apart AND are >30 mg/g would qualify
          - a. Even if there are multiple proteinuria measures in the E.H.R., and only two of them are >30 mg/g, but they are separated by at least 3 months would qualify
          - b. If there is only 1 proteinuria measure >30 mg/g and there are 2 or more proteinuria measures separated by 3 months within the prior 12 months would not qualify
        - 3) If there are not 2 proteinuria measures in 12 months, review within 24 months of enrollment.  
OR
      - C)  $15 \leq eGFR \leq 60$  ml/min for 2 time periods ≥ 3 months  
GFRs are taken within 12 months of enrollment, unless 2 values are unavailable, then review within 24 months.
        - 1) If there is only 1 GFR in E.H.R. (or if there are multiple and are all within 3 months), any single GFR between 15-60 would qualify
        - 2) If there are two or more GFRs in E.H.R. that are at least 3 months apart AND are between 15-60 would qualify

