## 5.2 Exclusion Criteria

- Have diabetes, but no CKD.
- Are currently on dialysis (ICD 10 codes N18.6, Z99.2 and Z94.0)
- Have ESRD (eGFR<15 ml/min)
- Have a left ventricular assist device (LVAD)
- Have a terminal illness (specifically metastatic cancer, palliative care or hospice)
- Have patient-reported known pregnancy at time of enrollment
- Have had a liver, kidney, or allogeneic bone marrow transplant
- Too cognitively impaired to provide informed consent and/or complete the study protocol
- Institutionalized or too ill to participate (i.e. incarcerated, psychiatric or nursing home facility)
- Plan to move out of the area within 6 months of enrollment
- Not a current patient seeing a provider who cares for their hypertension (i.e., family medicine, internal medicine, nephrology, HIV provider, cardiology, hypertension specialists) at a participating site
- Previously participated in the GUARDD pilot study OR have previously undergone *APOL1* testing

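### Secondary endpoint 5b lists E18.x where 5a and the eligibility criteria list N18.x: read literally, a participant with no baseline CKD code whose only new CKD code is N18.x is N on endpoints 5 and 6

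*Combined protocol and SAP*

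**What the plan says.** Section 3.2 names six secondary endpoints and points elsewhere for their rules: "Please see Section 10.2 for the derivations of these endpoints".

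In Section 10.2, the any-stage CKD endpoints are built as follows.

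- 5a (baseline) is Y if the record holds one of the codes "i.e., N18.x; E08.22; E09.22; E10.22; E11.22; E13.22) in the 24 months prior to baseline".
- 5b (6 months) is Y if it holds one of the codes "i.e., E18.x; E08.22; E09.22; E10.22; E11.22; E13.22) in the 6 months after baseline".
- Endpoint 5 is Y when 5a is N and 5b is Y.
- Endpoint 6 is Y when endpoint 5 is Y or 5a is Y.

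The stage 3 and above endpoints (3 and 4) have the same structure. Their baseline codes (3a) run from N18.3 to N18.5, and their follow-up codes (3b) from N18.3 to "N18.6 in the 6 months after baseline".

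The eligibility definition of CKD in the synopsis starts with "ICD10 codes (i.e., N18.x; E08.22; E09.22; E10.22; E11.22; E13.22", and Section 5.1 repeats that list. E18 appears nowhere else in the document, including the diabetes code table in Appendix A.

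Two entry rules bear on who could be affected. Participants must either "do not have diabetes and do not have CKD, or 2) have CKD", and Section 5.2 excludes those who "Have diabetes, but no CKD". Section 5.1 also admits people on laboratory evidence without any CKD code. For example, where there is only one urine measure, or all lie within 3 months, "any single proteinuria/microalbuminuria >30 mg/g would qualify".

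**The concern.** Endpoints 5 and 6 are the any-stage measures for secondary aim 1, the effect of knowing a positive *APOL1* status on documented CKD diagnosis. Once E18.x stands in for N18.x, the five codes left in 5b are E08.22, E09.22, E10.22, E11.22 and E13.22. All five are on the Appendix A diabetes list. As printed, 5b therefore has no route to Y through the general CKD codes that 5a, 3b and eligibility all use.

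Two things are at stake. First, new N18.x documentation would drop out of the any-stage measures for participants who had no CKD code at baseline, and only they can show a change on endpoint 5. Second, the endpoints would stop being nested: a participant could have a documented stage 3 or higher diagnosis while having no documented diagnosis of any stage.

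**Working it through.** The plan states no expected rate or power for endpoints 3 to 6, so there is no figure to reproduce. The check is one of logic, followed by simple scaling.

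**Step 1. Run the printed rules on code histories.** Inputs are rules 3a to 3c, 4, 5a to 5c and 6 of Section 10.2. They are applied once with 5b as printed and once with N18.x in 5b. I assume that no participant carries a code beginning E18, since the document names none elsewhere.

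| CKD codes before baseline | CKD codes after baseline | Endpoints 3, 4, 5, 6 as printed | Endpoints 3, 4, 5, 6 with N18.x |
|---|---|---|---|
| none | N18.1, N18.2 or N18.9 only | N, N, N, N | N, N, Y, Y |
| none | N18.3, N18.4, N18.5 or N18.6 only | Y, Y, N, N | Y, Y, Y, Y |
| none | N18.3 and E11.22 | Y, Y, Y, Y | Y, Y, Y, Y |
| none | E11.22 only | N, N, Y, Y | N, N, Y, Y |
| N18.2 | N18.3 | Y, Y, N, Y | Y, Y, N, Y |
| E11.22 | N18.3 | Y, Y, N, Y | Y, Y, N, Y |
| N18.3 | N18.3 | N, Y, N, Y | N, Y, N, Y |

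Only the first two rows change. The error acts when 5a is N and the new codes are N18.x without a listed diabetic-CKD code.

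**Step 2. Check nesting after correction.** With N18.x in 5b, every 3b code is a 5b code, and every 3a code is already a 5a code. So 3b = Y implies 5b = Y. Endpoint 4 = Y means 3a or 3b is Y, hence 5a or 5b is Y, hence endpoint 6 = Y. As printed, the second row violates both implications.

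**Step 3. Who has 5a = N.** This includes people who entered without CKD, who must also be free of diabetes. It also includes people who entered on laboratory criteria alone, with or without diabetes. Anyone in these groups who gains no diabetic-CKD code in follow-up cannot be Y on endpoint 5 under the literal rule.

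**Step 4. Scaling.** In one arm, let p5 be the correct endpoint 5 proportion and s the share of newly coded participants whose only new CKD codes are N18.x.

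- Literal endpoint 5 = (1 − s) × p5.
- Endpoint 6 = P(5a = Y) + p5, because the two groups do not overlap. Literal endpoint 6 is therefore lower by s × p5.
- Literal endpoint 5 difference, with subscript I for Intervention and C for Control, = (1 − s_I) × p5_I − (1 − s_C) × p5_C. If s_I = s_C = s, this equals (1 − s) × (p5_I − p5_C).

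The documents do not give s. Over its whole possible range:

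| s (assumed) | 0% | 25% | 50% | 75% | 100% |
|---|---|---|---|---|---|
| Share of correct endpoint 5 retained, 1 − s | 100% | 75% | 50% | 25% | 0% |

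Among participants with no diabetes code after baseline, s is 100% by construction, because every code left in 5b is a diabetes code.

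**The case against.** The strongest reply is that nobody would be misled. 5b itself speaks of a CKD code. The line above it gives N18.x followed by the same five codes in the same order, as do both eligibility lists. The detailed SAP and the extraction algorithms are separate documents, and nothing here shows that either uses E18.x. The letter could even be an artefact of converting the PDF to text, although N18.x came through correctly in 5a. Section 9.9 reports secondary endpoints as estimates with 95% confidence intervals and no p-values.

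Most of this stands. The intent is clear, and the harm is conditional. It does not remove the need for a correction: the entry is in the operative rule, no current section overrides it, and Section 7.7 lets sites adapt central code or write their own. A search on an unmatched code simply returns nothing, so an ordinary range or missing-value check need not reveal it.

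Some stronger readings are tempting, and the documents do not support them.

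- A reader might infer that every new N18.x code is lost. Rows three, five, six and seven of the first table show otherwise.
- A reader might take endpoint 3 = Y with endpoint 5 = N as a sign of the error. It also arises correctly, as when N18.2 is followed by N18.3.
- A reader might size the loss from the 40% under-documentation figure in Section 2.1. That figure concerns problem lists, not ICD codes, and does not give s.
- A reader might count the Section 7.7 collection window for CKD codes (up to 8 months) against the 6 months in 3b and 5b as further evidence. It can be read as a wider data pull containing a narrower counting window. It merits its own clarifying sentence and adds no weight here.

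**Conclusion.** The code list in 5b is wrong as written and should be corrected. Its effect is confined to participants with no 5a code in the 24 months before baseline whose only new CKD codes are N18.x. They become N on endpoints 5 and 6, and where the code is N18.3 to N18.6 this contradicts their Y on endpoints 3 and 4.

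The number of such participants cannot be computed from the documents. Proportionally, endpoint 5 would lose anything from nothing to all of its events as s runs from 0% to 100%. With equal s in both arms the difference shrinks towards zero by the factor (1 − s); with unequal s the direction of the error is unknown.

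The primary endpoint, endpoints 1 to 4, alpha and power are untouched. It would go too far to say that endpoints 5 and 6 will be misreported: that requires E18.x to have been carried into the SAP or an extraction query, and neither is available here.

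**What to change.** 1. Confirm the character in the source file, then replace E18.x with N18.x in 5b so that it matches 5a.
2. Confirm that the SAP and the central and site extraction algorithms search N18.x after baseline.
3. Add two programmed checks: 3b = Y implies 5b = Y, and endpoint 4 = Y implies endpoint 6 = Y. Do not add a check that endpoint 3 = Y implies endpoint 5 = Y, since that fails correctly for participants already coded at a lower stage.

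The cost is one corrected code in the protocol and a review of existing code. No new data are needed if the extractions already use N18.x. If any query used E18.x literally, that query must be rerun, which is easiest to settle before the final EHR download.
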